Upneeq[™] is an FDA approved drug for the treatment of ptosis. It is available in a drop formulation. This agent should be considered exempt from IND requirements as the study is using the drug in realm of FDA indications and meets the below IND criteria.

• The research is not intended to be reported to the FDA as a well-controlled study in support of a new indication for use nor intended to be used to support any other significant change in the labeling for the drug.

• The research is not intended to support a significant change in the advertising for the product.

• The research does not involve a route of administration or dosage level or use in a patient population or other factor that significantly increases the risks (or decreases the acceptability of the risks) associated with the use of the drug product.

• The research is conducted in compliance with the marketing limitations described in 21 CFR §312.7.

Drug insert is available and attached to the IRB protocol.

Procedures Involved

We anticipate that procedures listed below will take about 30 to 40 minutes per patient. Except as noted, the procedures below are not considered standard of care and are being conducted for the study alone.

Part 1: Pre-treatment data collection

- Patients will complete a pre-treatment survey to evaluate the perceived baseline eye appearance.
- Patients will undergo pre-treatment baseline photography. Images will be taken in a room with the same conditions.
- An Ipad (Apple Inc, Cupertino, California, U.S.A.) with the Upneeq software app will be used. This app directs subjects to a standardized position and distance from the Ipad to measure the MRD1 and MRD2 in each eye. The subjects will focus on the Ipad with their eyes in primary gaze.
- All photographs will be taken with the dedicated Ipad camera, which will use standardized aperture, shutter speed, and exposure time.
- Photographs will be recorded and saved as JPG files (1200 9 797 pixels, 24-bit, RGB) in a locked folder. When not in use, the Ipad and accompanying software will be secured in a locked drawer.

Part 2: Upneeq[™] application

- Subjects will be randomized to receive either Upneeq[™] or balanced saline placebo in both eyes.
- Based on the randomization results, the examiner will apply Upneeq[™] eye drops or saline to the subject's eyes.

Part 3: Post-treatment data collection

- Subjects will wait 2 hours after they receive eye drops.

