- Subjects will be photographed at 2 hours after drop instillation according to the procedure described above. This will allow Upneeq to reach its average time for maximum effect.
- Patients will complete a post-treatment survey to evaluate the perceived change in eye appearance following Upneeq[™] administration.

Part 4: Data analysis

- Data will be recorded and stored in a secure Microsoft Office Excel (Microsoft Corporation, Redmond, WA, U.S.A.) spreadsheet. Data will be graphically analyzed and represented with Adobe Photoshop (Adobe, Inc., San Jose, CA, U.S.A).
- Data assessed will involve assessing pre and post-treatment MRD1 and MRD2, investigator-assessed measurements of conjunctival color including the Validated Bulbar Redness Scale and patient-reported outcome measures such as those measured through the FACE-Q survey or other patient perceptions of the drop and changes in appearance before and after drop instillation.
- User performing analysis will be blinded to which patients received study drug or control.

No additional follow-up outside of the patient's next routine clinic visit will be needed. Patients who do have symptoms concerning any post-procedural complications will be instructed to notify study staff immediately. A phone number will be provided. Clinical examination post-procedure will be at Bascom Palmer Eye Institute.

Outcomes Measured

Primary outcome:

Outcome Measure Title: Change in palpebral fissure height

Outcome Measure Description: Palpebral fissure height will be calculated from the sum of marginal reflex distance 1 and 2 measured from the photograph by Ipad software and recorded by investigators.

Outcome Measure Timeframe: Baseline prior to drop administration, Day 1

Secondary outcomes:

Outcome Measure Title: Change in eye redness

Outcome Measure Description: Scoring of ocular redness from clinical photographs will be performed by investigators on a 0 - 100 unit scale as compared to standardized reference photographs (0 = no redness, 100 = very red). Images may also be analyzed quantitatively using software to calculate changes in redness between photographs.

Outcome Measure Timeframe: Baseline prior to drop administration, Day 1

Outcome Measure Title: Change in Patient-reported eye appearance

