Outcome Measure Description: Patient-reported eye appearance will be assessed by patient completion of the FACE-Q Eye Module Survey. These surveys have a total raw score of 7 (worst) to 28 (best). Higher scores indicate greater satisfaction. These survey scores will be

assessed individually. Additionally patients will be queried regarding their perception of the drop including changes in eye appearance before or after drop instillation. Outcome Measure Timeframe: Baseline prior to drop administration, Day 1

Adverse Events and Serious Adverse Events

Treatment-emergent adverse events, defined as any event not present prior to the initiation of the drug treatment or any event already present that worsens in either intensity or frequency following exposure to the drug treatment, will be monitored and reported throughout the study. Treatment emergent adverse scale will be graded as the following:

- Mild: Transient or mild discomfort (<48 hours) to the subject; no medical intervention/therapy required.

- Moderate: Mild to moderate limitation in activity of the subject; no or minimal medical intervention/therapy required.

- Severe: Marked limitation in activity of the subject, some assistance usually required; medical intervention/therapy required including possible hospitalization.

Serious adverse events are defined as those which result in death, hospitalization, persistent or significant incapacity or substantial disruption of the ability to conduct normal life functions (aka disability), or congenital anomaly / birth defect.

Previously reported treatment-emergent adverse effects are described further in the risks section below.

Withdrawal of Subjects

Patients may withdraw at any time at their discretion. Subject withdrawn from and/or terminated from research with or without their consent are those who are found to not meet inclusion/exclusion criteria, and/or are not able to complete the research protocol in its entirety, as well as those who suffer a treatment-emergent adverse effect requiring medication discontinuation. For any subjects who withdraw from research, including partial withdrawal from procedures, study data of the withdrawn subject will not be included in statistical analysis and will be shredded.

Data and Specimen Banking*

Not applicable.

Data Management*

Steps to Secure Data

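### The withdrawal rule drops and shreds the data of anyone who withdraws, even partially, so valid 2-hour primary values can be lost and adverse-event records are not exempted

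*Combined protocol and SAP*

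**What the plan says.** The rule is in the protocol section Withdrawal of Subjects, which has three steps.

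- Voluntary withdrawal: "Patients may withdraw at any time at their discretion".
- Removal on other grounds: a sentence beginning "Subject withdrawn from and/or terminated from research with or without their consent" lists subjects found not to meet the entry criteria and those who cannot complete the whole protocol, "as well as those who suffer a treatment-emergent adverse effect requiring medication discontinuation".
- Consequence: "For any subjects who withdraw from research, including partial withdrawal from procedures", the "study data of the withdrawn subject will not be included in statistical analysis and will be shredded". No exception is given.

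Other sections bear on how the rule works.

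- Procedures Involved puts the baseline survey and photograph in Part 1, and randomisation and the drops in Part 2. Part 3 has the 2-hour wait, then the photograph ("Subjects will be photographed at 2 hours after drop instillation"), then the post-treatment survey.
- Outcomes Measured derives the primary outcome, palpebral fissure height, from MRD1 plus MRD2 on the photograph. The survey plays no part in it.
- The Statistical Analysis Plan names no analysis population and no method for missing data.
- Adverse Events and Serious Adverse Events says that treatment-emergent events "will be monitored and reported throughout the study". Risks to Subjects sends unanticipated problems and complications to the IRB.

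**The concern.** In a randomised comparison, the analysed set should depend as little as possible on what happens after allocation. This rule does the reverse. It makes completion of every procedure a condition for having any data analysed, and it is the only statement in the documents about who is analysed.

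Three things are at stake.

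- **Primary values that already exist are thrown away** because a later, unrelated procedure was missed.
- **Membership of the analysed set can depend on events after randomisation**, including adverse effects, which could differ between oxymetazoline and saline.
- **The records are destroyed as well as excluded.** Exclusion alone could be examined later in a sensitivity analysis. Destruction may prevent that, and the sentence does not set apart adverse-event or allocation records.

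**Working it through.** **1. Whom the rule removes, and what is lost**

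| Subject | Covered by the rule? | 2-hour primary value? | Consequence |
|---|---|---|---|
| Photographed at 2 hours, then declines the survey | Yes, on any reading (partial withdrawal) | Yes | A complete primary value is removed |
| Leaves voluntarily during the 2-hour wait | Yes | No | No primary value to lose; other records are not exempted |
| Found ineligible | By inference | Possibly, if found late | A value may be removed |
| Cannot complete the protocol | By inference | Depends on when | No effect on the randomised comparison if before Part 2; selection after randomisation if later |
| Adverse effect requiring discontinuation | By inference | Possibly | A value may be removed for a reason that could differ by arm |

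The last three rows are inferred because the consequence is worded for subjects who withdraw, while the preceding sentence describes subjects withdrawn or terminated. The inference is natural: the consequence goes on to speak of the withdrawn subject directly after that list.

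**2. Primary values lost**

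The only input is the planned total of 114 (Statistical Analysis Plan; Local Number of Subjects). The documents give no effect size, SD, power or withdrawal allowance behind it, so it cannot be reproduced. It serves here only as a denominator.

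- One survey-only refusal: 1/114 = 0.9%.
- Five: 5/114 = 4.4%.

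**3. Illustration of precision and bias**

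The Statistical Analysis Plan specifies a paired t-test and no between-arm comparison. The figures below therefore illustrate a contrast that the plan does not specify. Further assumptions, none from the documents: 57 per arm (114/2), equal SDs set to 1, and all m removals from one arm.

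- Standard error (SE) of the difference with nobody removed: sqrt(2/57) = 0.187 SD.
- SE inflation: sqrt[(1/57 + 1/(57 − m)) / (2/57)] − 1. This is 0.4% for m = 1 and 2.4% for m = 5.
- Shift in that arm's mean: (m/57) × k, where k is the difference in SD units between those removed and those kept.

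| m | k | Shift (SD) | Share of 0.187 |
|---|---|---|---|
| 1 | 0.5 | 0.009 | 5% |
| 1 | 1 | 0.018 | 9% |
| 5 | 0.5 | 0.044 | 23% |
| 5 | 1 | 0.088 | 47% |

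If refusing the survey has nothing to do with lid position, k = 0 and only precision is lost. The shift needs removals that are both lopsided by arm and related to outcome.

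**4. Illustration for safety, only if adverse-event records are destroyed**

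With 57 in an arm and one subject withdrawn for an event, the true count is 1/57 = 1.8% (exact 95% CI 0.04% to 9.4%). With that subject's records gone it would appear as 0/56 = 0% (0% to 6.4%).

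**5. What the two key terms cover**

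*Study data* is not defined. Nor is *shredded*: "Photographs will be recorded and saved as JPG files", results are held in a spreadsheet (Procedures Involved, Part 4), and the section on privacy provisions lists paper shredding and electronic erasure as separate acts. The text does not settle whether electronic files are destroyed.

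**The case against.** The strongest reply is that little can go wrong in practice. The study gives one application, measures at 2 hours and calls itself a pilot. Few subjects will withdraw, and stopping medication has little scope after a single application. Destruction may also reflect what subjects were promised; the consent pages are not in this copy. Most of this stands. It limits the size of the problem and means that the consent must be checked. It does not justify discarding a primary value already obtained from a subject who has not asked for it to be removed.

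A reader might also infer several stronger points that the documents do not support.

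- **That adverse events in withdrawn subjects will go unreported.** The text does not say so. Two sections separately require reporting, and events could be reported before records are destroyed. The supportable statement is that these records are not exempted.
- **That every removal for non-completion happens after randomisation.** The baseline survey and photograph precede allocation, so some non-completion can occur earlier and cannot bias the comparison.
- **That bias of 23% to 47% of a standard error is to be expected.** Those figures need five removals, all in one arm, differing by 0.5 to 1 SD. The documents support none of these inputs.
- **That shredding contradicts a three-year retention commitment.** That line under Confidentiality is an item in a tick-box list, and the ticks are not visible in this copy.

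**Conclusion.** The point holds, and the rule should be changed. It is firmest for partial withdrawal: a subject with a 2-hour photograph who declines the survey loses a valid primary value however the rule is read. Its extension to ineligible, incomplete and adverse-effect subjects rests on the natural reading rather than on explicit words. Where it applies, some of those grounds can arise after randomisation and could differ by arm.

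The only magnitude that follows from the documents is the loss per subject in step 2. The actual bias cannot be computed, because no withdrawal rate, allocation ratio or outcome SD is given, and it is probably small. The standard-error, shift and safety figures are illustrations under the assumptions stated with them. On safety, the finding is an undefined scope that leaves adverse-event and allocation records unprotected, not a demonstrated loss.

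**What to change.** 1. Replace the sentence in Withdrawal of Subjects so that data collected up to withdrawal are retained and analysed unless the subject revokes permission. Check that the consent wording matches.
2. State in the Statistical Analysis Plan that the primary analysis includes all randomised subjects with a 2-hour measurement, in the arm assigned. Make any analysis that leaves out ineligible or incomplete subjects a sensitivity analysis.
3. Tabulate by arm the withdrawals with reasons and the number without a 2-hour value. Step 2 recovers only subjects who were photographed. Those who leave earlier remain missing, so this table is needed to judge any remaining selection. A sensitivity analysis for the missing values is optional.
4. State that allocation and adverse-event records are kept for everyone who received a drop, and reconcile the shredding rule with the statement that treatment-emergent events are monitored and reported.
5. Define *study data*, and say whether *shredded* includes electronic files, wherever any destruction rule remains.

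The cost is protocol and SAP wording, retention of a few more coded records, one short table and possibly a change to the consent. No extra visits or subjects are needed. For anyone already enrolled, what can be kept depends on the consent they signed.

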Improvement in eyelid position and eye redness may lead to subjective patient-reported improvement in cosmesis, which may be important for improvement in self-confidence, psychological well-being, and increased comfort in social settings.²⁶ Prior studies investigating the effect of surgical ptosis repair have reported improvement in perceived eye appearance. However, no study has yet evaluated the effect of medical management of eyelid position on subjective eye appearance. The FACE-Q is a patient-reported outcome measurement developed to address the lack of instruments for facial aesthetic procedures.²⁷⁻³⁰ FACE-Q has been previously reported as one of only 3 patient-reported outcome measures that met international recommendations for how such tools should be developed and validated per Oxford review of cosmetic surgery patient-reported outcome measures.²⁹ It has been used to evaluate patient-reported outcomes associated with multiple facial surgical procedures including botulinum toxin injections, blepharoplasties, and other cosmetic eye treatments.^{29,31,32} Therefore, the FACE-Q may be a useful, well-validated method of measuring patient perception of eye appearance following administration of topical medications that may result in improved cosmesis.

To the authors' knowledge, there are currently no randomized control trials objectively observing the effects of oxymetazoline on eye redness. Additionally, further studies are needed to better evaluate the effect of oxymetazoline on palpebral fissure height and the potential variability of this effect in different individuals, including those with different eyelid positions. Lastly, no studies have evaluated patient-reported aesthetic appearance before and after oxymetazoline use. In this randomized controlled study, we aim to record changes in palpebral fissure height and eye redness before and after administration of 0.1% oxymetazoline ophthalmic solution, aiming to gain a deeper understanding of oxymetazoline's therapeutic potential as well as evaluate patient-reported subjective changes in appearance.

Inclusion and Exclusion Criteria*

Inclusion Criteria

- Adults age 18 and above able to provide informed consent to participate
- Subject with stable ocular health, defined as no ocular conditions requiring ongoing topical therapy or recent surgical intervention

Exclusion Criteria

- Adults unable to consent
- Individuals less than 18 years of age
- Prisoners
- Pregnant women.

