The study coordinator will assign each patient a specific ID number and place this information on a separate spreadsheet. The study coordinator will collect the sex, patient's age, and dates of service, but no other identifiable information. No names will be used in the forms. Presentations and publications will not identify individual patients. Data from the subjects' medical records will be encrypted and stored securely as detailed below. Identifiable data will not be stored for future use beyond the timeframe of this study. The release of data will be only to study members and no other outside organization. Data will be kept under lock and key in [name] office at the Bascom Palmer Eye Institute Oculoplastics Research Laboratory on the 4th floor ([name]), data encoded in the computer will be password-protected and will be available only to study personnel, and protected health information will not be re-used or disclosed for other purposes. Study members will be trained on how to log in and log out of the computers. The study coordinator will assign each patient a specific ID number and the sex, patient's age and date of on a separate spreadsheet. The study coordinator will record the study results with the specific sample ID on another spreadsheet.

Statistical Analysis Plan

Statistical analysis will be performed by the researchers. A paired t-test will be used to analyze the difference in palpebral fissure height, eye redness, and patient-reported eye appearance as measured through the FACE-Q survey. 114 subjects will be required to perform perimetric statistics. Chi-squared testing will be used to assess categorical variables. P <0.05 will be considered significant.

Risks to Subjects*

The primary risks to the subjects are adverse reactions to the medication. These risks are explained to patients prior to their arrival to the Oculoplastics Clinic. Previously described potential adverse reactions to include instillation site discomfort, punctate keratitis, and blurry vision although in general is well-tolerated.^{21–23,33} Potential psychosocial risks to subjects include time taken from their day to undergo tests, potentially missing work, and anxiety or discomfort from the eye drop instillation process. This study is not collecting sensitive information, thus no potential risk to reputation or legal risks should occur.

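### The SAP specifies no drug-versus-placebo comparison for fissure height, redness or FACE-Q; its only test for them is a paired t-test, which cannot supply one in this design

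*Combined protocol and SAP*

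**What the plan says.** The Statistical Analysis Plan section is one short paragraph. For the continuous outcomes it states: "A paired t-test will be used to analyze the difference in palpebral fissure height, eye redness, and patient-reported eye appearance". It does not say what is paired with what, or which arm or arms enter the test. The only other test is for a different type of data: "Chi-squared testing will be used to assess categorical variables". Significance is set at P<0.05.

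The design is described elsewhere:

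- Procedures Involved, Part 2: the subject is randomised to Upneeq "or balanced saline placebo in both eyes". No crossover, fellow-eye control or matching of subjects is described.
- Procedures Involved, Part 1: the app is used "to measure the MRD1 and MRD2 in each eye", so fissure height is available for two eyes per subject.
- Procedures Involved, Part 4: "User performing analysis will be blinded to which patients received study drug or control". No test is named there.
- Background: "In this randomized controlled study, we aim to record changes in palpebral fissure height and eye redness before and after administration".
- Objectives: all three aims, and the hypothesis, concern the effect of the drug.

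**The concern.** A placebo arm exists so that the change on drug can be set against the change on saline. The SAP gives the saline arm no role in analysing the primary outcome or the scored secondary outcomes. If the paired test is run as written, a shift that has nothing to do with the drug can be reported as a drug effect. Such a shift could come from expectation, repeat measurement, or the two-hour wait. It is more plausible for FACE-Q and investigator-scored redness than for software-measured fissure height.

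The gap also leaves the choice of comparison, and of eye or subject as the unit, open until the data are in hand.

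**Working it through.** **The plan's own figure.** The only number in the SAP that could reveal the intended comparison is the sample size of 114. It cannot be reproduced, because no effect size, SD, power, allocation ratio or dropout allowance is given. It therefore does not show whether a paired or a two-sample test was in mind.

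**What each reading estimates.** Let Δ_D and Δ_P be the true mean changes on drug and on saline, and w the fraction of subjects on drug. The aims call for Δ_D − Δ_P.

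| Reading of the paired test | What it estimates or tests |
|---|---|
| Before/after, drug arm only | Δ_D |
| Before/after, all subjects pooled | wΔ_D + (1 − w)Δ_P |
| Before/after, each arm separately | Δ_D = 0 and Δ_P = 0, as two separate tests |
| Right eye/left eye | Difference between two eyes given the same drop |

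None of these is a test of Δ_D − Δ_P. The first coincides with it only if Δ_P = 0, which the analysis would assume and not check. If Δ_P = 0, the pooled estimate is wΔ_D: half the drug effect at 1:1 allocation and two thirds at 2:1. Finding one arm significant and the other not is not a test of the difference between them.

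**Size of the error if there is a shift.** These inputs are assumptions, not figures from the documents: 57 per arm (114/2), two-sided 0.05, no drug effect, and an equal shift of d SDs of change in both arms. The paired t-test rejects with probability P(|T| > t_crit), where T is noncentral t with n − 1 degrees of freedom and noncentrality d√n. For n = 57, t_crit = 2.003; at d = 0.25 the noncentrality is 0.25 × √57 = 1.89, giving 0.458. Call the n = 57 probability p. The arms are independent, so 'drug significant, placebo not' has probability p(1 − p), which cannot exceed 0.25.

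| Shift d | Drug arm, n = 57 (p) | Pooled, n = 114 | Drug significant, placebo not, p(1 − p) |
|---|---|---|---|
| 0 | 5.0% | 5.0% | 4.8% |
| 0.05 | 6.6% | 8.3% | 6.2% |
| 0.1 | 11.5% | 18.5% | 10.2% |
| 0.2 | 32% | 56% | 22% |
| 0.25 | 46% | 75% | 25% |
| 0.5 | 96% | >99% | 4% |

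The allocation ratio is not stated. With 38 or 76 subjects on drug, the drug-arm figure at d = 0.25 is 32% or 58%.

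**The comparison that should be there.** In 40,000 simulated trials per setting, a two-sample t-test of change rejected in 5.1%, 5.0%, 5.0% and 4.9% of trials at d = 0, 0.1, 0.25 and 0.5. A shift common to both arms cancels.

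**The case against.** The strongest reply is that the SAP is loosely worded, not wrong. It refers to a difference without saying between what. Randomisation, a saline arm and a blinded analyst all suggest that the arms were meant to be compared. The Background words the aim as change before and after the drop, and a paired test does answer that. The study also calls itself a pilot and says it is not meant to support a new indication or a labelling change.

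Part of this stands. Intent to compare can be inferred, and the pilot status softens the consequences. But the one test named cannot be applied to two independent groups, so the intended comparison cannot be read out of the text. The before/after wording in the Background does not override aims and a hypothesis about the drug's effect, and the plan still applies P<0.05.

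Three further limits are fair:

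- The point covers fissure height, redness scores and FACE-Q scores. Categorical answers about the drop could be compared between arms by chi-squared, although the SAP does not say so.
- The rejection rates are illustrations. The high ones need shifts of 0.25 to 0.5 SD, which are less plausible for the primary outcome than for the other two. The rates are also two-sided, so at zero shift half of the 5% lies in the unfavourable direction.
- ANCOVA is a preference. Any valid subject-level comparison of the arms removes the error.

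**Conclusion.** The concern holds and must be fixed. No between-arm comparison is specified for any continuous outcome, including the primary, and the named test cannot provide one under this design. That conclusion rests on the text alone and does not depend on the size of any placebo shift.

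False-positive inflation is a second problem and arises only if there is a shift. Under the stated assumptions it is modest at 0.05 to 0.1 SD (6.6% to 11.5% for the drug-arm test) and severe at 0.25 SD and above (46% or more).

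**What to change.** Replace the paired t-test sentence with text to this effect:

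- Each continuous outcome is compared between randomised arms at subject level by ANCOVA, with the 2-hour value as response, arm as factor and that outcome's baseline as covariate. Report the adjusted difference (drug minus placebo), its 95% confidence interval and a two-sided p-value. A two-sample t-test of change is an acceptable simpler choice.
- For outcomes measured by eye (fissure height, and redness if scored by eye), analyse the mean of the two eyes, or both eyes with the within-subject correlation modelled. FACE-Q is one score per subject.
- Within-arm paired tests are descriptive only.

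The unit of analysis should be fixed in the same paragraph. The plan does not say that eyes will be treated as independent, but it does not rule this out. In 20,000 simulated trials per setting with no effect, a two-sample test on 2 × 114 = 228 eyes treated as independent rejected about 5%, 11% and 16% of the time at assumed between-eye correlations of change of 0, 0.5 and 0.9.

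The cost is one paragraph. Baseline and 2-hour data are already collected, and the change of test does not itself require more subjects. There is an apparent loss of precision. At 80% power and two-sided 0.05, the detectable effect is 0.26 SD for a paired test in 114 and 0.38 SD for one in 57, against 0.53 SD for a two-sample test at 57 per arm. The smaller figures answer a different question, so nothing relevant to the aims is lost. Because the plan states no target effect or power, whether 114 is enough for the between-arm test cannot be judged; the sample size statement should be rewritten for that test. The reported effect will be net of any placebo change and may look smaller.
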